#### **14.4.2 Secondary Efficacy Analyses**

The following endpoints will be considered exploratory and no corrections for multiple comparisons will be made:

*CGM derived indices and HbA1c metrics:*

- Time spent above target glucose (10.0 mmol/l) (180 mg/dl)
- HbA1c at 18 months
- Average of glucose levels
- Time spent below target glucose (3.9 mmol/l) (70 mg/dl)
- Standard deviation, and coefficient of variation of glucose levels
- Time with glucose levels <3.0 mmol/l (54 mg/dl)
- Time with glucose levels in significant hyperglycaemia (glucose levels > 16.7 mmol/l) (300 mg/dl)

*Insulin and Other Endpoints:*

- BMI SDS
- Total, basal, and bolus insulin dose

*Questionnaire Scores:*

- Strengths and Difficulties Questionnaire
- Hypoglycaemia Fear Survey
- WHO-5

- Epworth Sleepiness Scale
- INSPIRE Survey

Analysis of all secondary CGM, HbA1c and insulin endpoints will parallel the primary analysis.

A ranked normal score transformation will be applied to all highly skewed secondary endpoints. For HbA1c and the CGM metrics, summary statistics will be reported every three months.

Summary statistics for the following outcome metrics will also be tabulated separately for daytime (defined as 8am to less than 12pm) and night time (defined as 12pm to less than 8am) over the 18-month period:

- Percent time with glucose levels spent in the target range (3.9 to 10.0 mmol/l)
- Mean of glucose levels
- Standard deviation of glucose levels
- Percent time with glucose levels below 3.9 mmol/l
- Total insulin dose

## 14.5 Safety Analyses

For each of the following safety outcomes, mean  $\pm$  SD or summary statistics appropriate to the distribution will be tabulated by treatment group:

- Number of subjects with any diabetic ketoacidosis events
- Number of episodes of diabetic ketoacidosis events per subject and incidence rate per 100 person years
- Number of subjects with any severe hypoglycaemia events
- Number of episodes of severe hypoglycaemia events per subject and incidence rate per 100 person years
- Number of adverse events per subject
- Number of serious adverse events per subject

For purposes of analysis, a severe hypoglycaemic event will be defined as described in section 11.2.3.

All of the above safety outcomes will be tabulated for all subjects (including dropouts and withdrawals), regardless of whether CGM data are available and irrespective of whether closed loop was operational. All adverse events will be listed for the entire study duration, including run-in and washout period.

For each of diabetic ketoacidosis and severe hypoglycaemia (if enough events), the event rates will be compared using a repeated measures Poisson regression model adjusting for period. Binary variables will also be compared using a repeated measures logistic regression model adjusting for period.

## **14.6 Utility Evaluation**

The amount of CGM use will be tabulated for each treatment arm, in addition to the amount of closed loop system use in the CL arm and the extension phase. Summary statistics appropriate to the distribution and range will be reported for the percentage of time using the CGM over the four month period (as defined above) for each treatment group. The same will be done for the percentage of time using the closed loop system in the CL arm and the extension phase. Tabulations of summary statistics will also be performed for the percentage of time spent using the closed loop system while using the CGM in the CL arm and the extension phase.

## **14.7 Questionnaires**

For each questionnaire (and their corresponding subscales), total scores will be calculated and reported at each time point. They will also be compared between treatment arms and with the sensor augmented pump therapy arm in the extension phase using the same model described above for the primary endpoint. The distribution of responses for each individual question at each time point will also be reported in a separate table.

## **14.8 Sleep assessment**

Sleep will be automatically scored by Actiware software using previously described and validated algorithms. Sleep duration will be calculated as the sum of all epochs scored as sleep during the time in bed. Variability across nights in a parent/guardian's sleep duration will be summarised using the coefficient of variation.

## **14.9 Interviews**

To maximise rigour at least two experienced qualitative researchers will be involved in data analysis. A thematic analysis will be undertaken by these individuals who will independently review data and write separate reports before attending regular meetings to compare their interpretations and reach agreement on recurrent themes

and findings. Interviews conducted in German will be translated and transcribed into English prior to data analysis.

Interviews will be read through repeatedly and cross-compared in order to identify issues and themes which cut across different participant's accounts.

A key aspect of the analysis will involve comparison of the experiences and views of participants in the sensor augmented pump therapy arm and closed loop arm of the study, to better understand the impact of closed loop as compared to sensor augmented pump therapy on diabetes self-management practices and quality of life. A final coding frame, reflecting the initial research questions and emergent themes, will be developed once all data have been reviewed and consensus reached on key themes and findings. NVivo9, a qualitative software package, will be used to facilitate data coding/retrieval.

## **14.10 Health Economics Evaluation**

For each simulation, a simulated cohort of 1,000 patients will be run through the model 1,000 times using first-order Monte Carlo simulation. Long-term outcomes will include total direct costs, life expectancy, quality-adjusted life expectancy and time to onset of complications. Future costs and clinical benefits will be discounted based on each country recommendations. The mean values from the simulation (a total of 1,000 mean values, each from a cohort of 1,000 patients run through the model) will then be used to generate scatterplots of incremental costs versus incremental effectiveness (quality-adjusted life years [QALYs]) for closed loop vs. sensor augmented pump therapy. Data from the scatterplot will then be used to generate a cost-effectiveness acceptability curve.

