## 12.6 Health Economics

The analysis will be performed using the IQVIA Core Diabetes Model (CDM; QVIA, Basel, Switzerland). The CDM is a validated non-product-specific policy analysis tool for cost-effectiveness analysis in both type 1 and type 2 diabetes; a detailed description of the model architecture (including schematic diagrams) and validation is available in publications by Palmer et al (67, 68) and more recently McEwan et al (69). In summary, the model is based on a series of inter-dependent submodels that simulate both acute and long-term diabetes-related complications (angina, myocardial infarction, congestive heart failure, stroke, peripheral vascular disease, diabetic retinopathy, macula oedema, cataract, hypoglycaemia, ketoacidosis, lactic acidosis, depression, oedema, nephropathy and end-stage renal disease, neuropathy, foot ulcer and amputation, and non-specific mortality). The sub-models have a semi-Markov structure and use time, state, time-in-state and diabetes type-dependent probabilities derived from published sources to simulate disease progression. Monte Carlo simulation using tracker variables is used to overcome the memory-less properties of the standard Markov model and allows for interconnectivity and interaction between individual sub-models.

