### 12.6.1 Simulation cohort and treatment effects

Baseline characteristics of the simulation cohort will come from the study. They will include: age, sex ratio, Hb1Ac and other risk factors. Treatment effects will be based on the study findings comparing 4 months of closed-loop with 4 months of sensor augmented pump therapy.

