### 12.6.2 Costs and utilities

Country specific direct costs will be sourced from published literature and where necessary inflated to the current year costs.

For treatment costs, only the incremental costs between the two arms will be considered, namely the difference between closed-loop therapy and sensor augmented pump therapy.

Health state utility values will be taken from published literature (70) and references therein.

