### *Sensitivity analysis*

In order to explore the robustness of the base-case findings and establish the key drivers of results, a series of one-way simulations will be performed on those parameters.

Additional exploratory health-economic analysis might be conducted on other endpoints such as but not limited to sleep disorders and indirect costs for the society.

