310 The electronic data capture system for this study will not allow the subject to submit any  
311 questionnaires until all items are completed. Analysis will be limited to subjects who submit a  
312 questionnaire (no imputation).

313 **7.7 Ancillary Analyses**

314 Cost utility analyses and human factors analyses will be described in a separate document.

315 **8. Safety Analyses**

316 All safety outcomes will be tabulated by participant for all events from enrollment to the final  
317 study visit.

318 **8.1 Definitions**

319 Reportable adverse events for this protocol include any untoward medical occurrence,  
320 unintended disease or injury, or untoward clinical signs (including abnormal laboratory findings)  
321 in a subject who has received an investigational device, whether or not related to the  
322 investigational medical device. These include severe hypoglycemia (SH) and diabetic  
323 ketoacidosis (DKA).

324 Hypoglycemic events will be considered severe if the event requires assistance of another person  
325 due to altered consciousness to actively administer carbohydrate, glucagon, or other resuscitative  
326 actions. This means that the subject is impaired cognitively to the point that he/she is unable to  
327 treat him- or herself, is unable to verbalize his or her needs, is incoherent, disoriented, and/or  
328 combative, or experiences seizure or coma. If plasma glucose measurements are not available  
329 during such an event, neurological recovery attributable to the restoration of plasma glucose to

330 normal is considered sufficient evidence that the event was induced by a low plasma glucose  
331 concentration.

332 Definite DKA is defined as having all of the following:

- 333 • Hyperglycemia (blood glucose >200 mg/dL or >11 mmol/L)
- 334 • with either low pH (<7.3) or low serum bicarbonate (<15 mmol/L)
- 335 • and ketonemia or ketonuria

336 **8.2 Adverse Events Summary**

337 All episodes of SH and of DKA along with any other reportable adverse events will be listed by  
338 treatment group.

339 Separate listings will be provided for pre-randomization and post-randomization adverse events.  
340 A separate listing also will be provided for events that occur during the extension phase.

341 **8.3 Comparison of Safety Outcomes between Treatment Groups**

342 The following safety analyses will be performed if enough events occur for formal statistical  
343 analyses.

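### Protocol 14.10 builds the cost-effectiveness acceptability curve from first-order simulation means, with no stated route for uncertainty in treatment effect, costs or utilities

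*Combined protocol and SAP*

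**What the plan says.** Protocol 14.10 (Health Economics Evaluation) states that "a simulated cohort of 1,000 patients will be run through the model 1,000 times using first-order Monte Carlo simulation". The 1,000 resulting means are plotted as incremental cost against incremental QALYs, and "Data from the scatterplot will then be used to generate a cost-effectiveness acceptability curve".

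The inputs are described in protocol 12.6:

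- Role of simulation (12.6): "Monte Carlo simulation using tracker variables is used to overcome the memory-less properties of the standard Markov model". This is patient-level tracking.
- Treatment effect (12.6.1): "Treatment effects will be based on the study findings comparing 4 months of closed-loop with 4 months of sensor augmented pump therapy".
- Costs (12.6.2): "Country specific direct costs will be sourced from published literature and where necessary inflated to the current year costs".
- Utilities (12.6.2): "Health state utility values will be taken from published literature (70) and references therein".

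No distribution, standard error, bootstrap or second-order sampling is named for any of these. The sensitivity analysis under 14.10 adds that "a series of one-way simulations will be performed on those parameters", without naming the parameters and without linking those runs to the curve. Protocol 10.7 only lists outcomes. SAP 7.7 says "Cost utility analyses and human factors analyses will be described in a separate document"; that document was not supplied.

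**The concern.** First-order Monte Carlo simulates random variation between patients at fixed model inputs. If the inputs stay fixed across the 1,000 runs, the cohort means differ only through that variation, and they draw together as the simulated cohort grows. Parameter uncertainty, meaning how well the trial and the literature pin down the effect, costs and utilities, does not enter.

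Protocol 5.5 gives the purpose as informing reimbursement decisions. A payer will read the curve as the probability that closed loop is cost-effective given the evidence. Two results that need no assumed figure show that a curve built this way cannot be read so. A trial half or twice as large with the same point estimates would give the same curve. Changing the simulated cohort size would change the curve although the evidence had not changed.

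**Working it through.** **What can be settled from the text.** The steps in 14.10 are complete: first-order runs, cohort means, scatterplot, curve. None redraws an input. With fixed inputs, the standard error of a cohort-mean net benefit is the per-patient SD divided by √N, where N is the simulated cohort size. No term for trial size appears.

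**What cannot be settled.** The documents do not give the per-patient SD of incremental net benefit, the net-benefit margin, or the standard error of the effect entered in the model. What follows is an illustration on assumed ranges under a normal approximation, with net benefit scaled by the valued QALY gain:

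- m, margin as a share of the gain: 0.05, 0.20, 0.60
- r, per-patient SD divided by the gain (scatter in incremental cost included): 2, 6, 14
- s, relative standard error of the treatment effect: 0.15, 0.30, 0.45
- N: 1,000 as planned

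**Scale for s.** Protocol 14.12 gives SD 10.3, correlation 0.3, effect 5 points and n = 65. The SD of the paired difference is 10.3 × √(2 × 0.7) = 12.19. With a paired t-test at two-sided 0.05, 65 subjects give 90.3% power and 64 give 89.8%, so the plan's 65 is reproduced. The standard error is 12.19/√65 = 1.51 points, or 1.51/5 = 30% of the effect. This is for time in range. The protocol does not say which trial result enters the model, so 30% is only a guide to scale.

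**First-order only: Φ(m√N/r), N = 1,000**

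| m | r = 2 | r = 6 | r = 14 |
|---|---|---|---|
| 0.05 | 0.785 | 0.604 | 0.545 |
| 0.20 | 0.999 | 0.854 | 0.674 |
| 0.60 | 1.000 | 0.999 | 0.912 |

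**Treatment-effect uncertainty only: Φ(m/s)**

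| m | s = 0.15 | s = 0.30 | s = 0.45 |
|---|---|---|---|
| 0.05 | 0.631 | 0.566 | 0.544 |
| 0.20 | 0.909 | 0.748 | 0.672 |
| 0.60 | 1.000 | 0.977 | 0.909 |

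A simulation with 400,000 draws at r = 6, N = 1,000, s = 0.30 gave 0.604 against 0.567, 0.854 against 0.749, and 0.999 against 0.977, in agreement with the formulas.

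**Dependence on simulated cohort size** (m = 0.20, r = 6). At N = 250, 1,000 and 4,000 the first-order probability is 0.701, 0.854 and 0.982.

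**Dependence on trial size** (m = 0.20, r = 6, N = 1,000). For a trial half, equal to or double the planned size, s is 0.30 × √2 = 0.424, 0.30 and 0.30/√2 = 0.212. The effect-only probability is 0.681, 0.748 and 0.827. The first-order probability is 0.854 each time.

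**Direction.** For a positive margin, first-order spread is narrower than effect uncertainty when r/√N < s, that is r < s√1,000. The limits are 4.7, 9.5 and 14.2 for s = 0.15, 0.30 and 0.45. Below the limit the first-order curve is overconfident; above it, too diffuse. With independent inputs and a positive margin, adding cost and utility uncertainty moves the reference towards 0.5, so the effect-only figures are upper limits for the full curve.

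**The case against.** The strongest reply is that the governing detail lies elsewhere. SAP 7.7 assigns the cost-utility analysis to a separate document, and protocol 12.6 refers to publications for the model's architecture. Protocol 14.10 never says that inputs are held fixed, and first-order may be loose wording for runs that also sample parameters. This stands as a limit on the claim, which covers only what the protocol and SAP state. It does not cure 14.10, which sets out a specific method from simulation to curve. If the other document samples parameters, 14.10 describes a different analysis and needs to be aligned.

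Parameter uncertainty is also not wholly ignored, because one-way simulations are planned and would be reported beside the curve. That is true, but nothing says that they feed the curve, and varying one input at a time does not give a joint probability.

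The illustration rests on assumed inputs, and its sign can reverse. At m = 0.20, r = 14 and s = 0.15 the first-order figure is 0.674 against 0.909; at s = 0.45 it is 0.674 against 0.672, practically no difference. The range for r is also open. A QALY gain of 0.2 to 1.0 with a patient-level SD of 2 to 8 and independent arms implies r = SD × √2/gain, or about 2.8 to 57, and a first-order probability of 0.55 to 0.99 at m = 0.20. All of this stands: no single size of error can be claimed. The structural fault, a spread that depends on N and not on trial precision, holds whatever these values are.

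**Conclusion.** The point holds. Followed as written, protocol 14.10 yields a curve that does not measure the decision uncertainty it will be taken to show. The conclusion rests on the ordinary meaning of first-order simulation and on the absence of any stated input sampling in the protocol or SAP; it would be answered if the separate document specifies such sampling.

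Size and direction cannot be derived from the documents. Over the assumed ranges at N = 1,000, the first-order probability runs from 0.545 to 0.785, 0.674 to 0.999 and 0.912 to 1.000 for margins of 5%, 20% and 60%. With effect uncertainty only, it runs from 0.544 to 0.631, 0.672 to 0.909 and 0.909 to 1.000. The output is ancillary, but health economics is a stated study objective, so this should be corrected before the curve is reported.

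**What to change.** Amend protocol 14.10 as follows:

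1. At each of the 1,000 outer runs, draw the treatment effect (trial estimate and standard error), costs and utilities from stated distributions.
2. Choose a cohort size that keeps residual first-order noise small by a stated criterion, for example adding no more than 5% to the SD of net benefit.
3. Build the scatterplot and acceptability curve from those draws.
4. Keep the one-way analyses for identifying key drivers, and name the parameters they vary.
5. If the document named in SAP 7.7 already specifies this, align 14.10 with it and cite it.

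The change can be made after data collection and needs no new data. The costs are specifying the distributions and possibly more computing. Against effect uncertainty alone, the 5% example requires N ≥ (r/(s√(1.05² − 1)))². That is about 190 patients per cohort at r = 2, s = 0.45; about 3,900 at r = 6, s = 0.30; and about 85,000 at r = 14, s = 0.15. The planned 1,000 may or may not be enough. Including cost and utility uncertainty lowers these figures. The curve may move in either direction.

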### *Sensitivity analysis*

In order to explore the robustness of the base-case findings and establish the key drivers of results, a series of one-way simulations will be performed on those parameters.

Additional exploratory health-economic analysis might be conducted on other endpoints such as but not limited to sleep disorders and indirect costs for the society.

## **14.11 Interim Analysis**

No formal interim analyses or stopping guidelines are planned for this study.

## **14.12 Sample Size and Power Calculations**

The study will run at seven sites. We have ensured adequate recruitment of participants and centres by allowing for a potential 50% uptake and 10% drop-out of participants among collaborative paediatric sites, with further contingency sites including participant identification sites (identified but not included as applicants).

Data from the SENCE study (NCT02912728) were used to estimate the standard deviation of the primary endpoint. Only subjects from the two treatment arms involving CGM use in this study who were using an insulin pump at the time of enrolment were used to estimate the SD. Based on data from this study, 65 subjects are required to attain 90% power to detect a difference if a treatment effect of 5%, a standard deviation of 10.3% for an individual measurement, and a correlation of 0.3 between periods are assumed. Adding an additional 10% to this sample size to account for drop outs results in a final sample size of 72 subjects.

## **14.13 Deviations from the Statistical Plan**

Any deviations from the original statistical plan will be recorded and agreed by the Investigators.

## **15 Case Report Forms**

The Case Report Form (CRF) is the printed, optical, or electronic document designed to record all the protocol required information to be reported to the Chief Investigator for each study subject.

CRFs will be completed in accordance with GCP and ISO 14551 Guidelines. Corrections to the CRF will be performed by striking through the incorrect entry and by writing the correct value next to the data that has been crossed out; each correction will be initialled and explained (if necessary) by the Investigator or the Investigator's authorised staff.

The electronic CRF system provides an edit feature that records the identity of the person making the change and retains a record of the before and after values of the data field(s) in question. In addition, all eCRF changes require electronic review and sign-off by the investigator associated with the visit.

If any amendments to the protocol or other study documents are made, CRFs will be reviewed to determine if an amendment to these forms is also necessary.

## **16 Data Management**

Confidentiality of subject data shall be observed at all times during the study. Personal details for each subject taking part in the research study and linking them to a unique identification number will be held locally on a study screening log in the Trial Master File at the investigation centre. These details will not be revealed at any other stage during the study, and all results will remain anonymous. The study identification number will be used on the case report forms and on all the blood and serum samples that are collected throughout the study. Names and addresses will not be used. Collected samples will be stored securely and locked away. Only researchers directly involved in the study will have access to the samples.

Electronic data will be stored on password-protected computers. All paper records will be kept in locked filing cabinets, in a secure office at the investigation centre. Only members of the research team and collaborating institutions will have password access to the anonymised electronic data. Only members of the research teams will have access to the filing cabinet. Paper copies of the data will be stored for at least 15 years in line with the General Data Protection Regulation (GDPR) (EU) 2016/679.

Direct access to the source data will be provided for monitoring, audits, REC review and regulatory authority inspections during and after the study. The fully anonymised data may be shared with third parties (EU or non-EU based) for the purposes of advancing management and treatment of diabetes.

Appropriate procedures agreed by the Chief Investigator and Principal Clinical Investigator will be put in place for data review, database cleaning and issuing and resolving data queries.

